Given these results, there is a need for additional therapies for patients with CMML, and especially those who have been previously treated with or are not expected to derive benefit from treatment with an HMA. Moreover, it has been recommended that “*every CMML patient be considered for clinical trials irrespective of risk stratification or treatment history because of limited prospective clinical data and the disease’s aggressive natural history.*” (Padron 2014).

Historically (including in the current study), given CMML’s original classification as an MDS, clinical studies enrolling CMML patients had responses measured via the International Working Group (IWG) response criteria for MDS. However, it was subsequently observed that approximately 50% of patients with CMML predominantly present with myeloproliferative, rather than myelodysplastic features (Loghavi 2018).

An international consortium of thought leaders recommended new response criteria to measure treatment response in MDS/MPN, including CMML, to capture measures of clinical benefit relating to CMML with proliferative features (Savona 2015) (see Table 8 in Appendix 18.1 for full response criteria). These revisions were justified by the authors, who indicated that “*the molecular and clinical heterogeneity and absence of uniform response criteria by which to assess meaningful therapeutic benefit make developing and comparing new therapies a challenge. Novel agents that target biological features important in MDS/MPN are in development; testing the effectiveness of these agents requires a harmonized assessment approach designed specifically for MDS/MPN*”.

One publication reports a retrospective validation of the revised criteria by outcome analysis of 79 patients with CMML. In this analysis, response status between the IWG 2006 criteria and newer MDS/MPN criteria was concordant in 86% of cases, and both sets of response criteria led to similar predictive power for OS. Notably, the more stringent definition of progression by the

MDS/MPN criteria was described by the authors as ‘relevant’, as 6 patients who had PD per the IWG 2006 criteria at first assessment finally achieved response, whereas no patients with progression per overlap-MDS/MPN achieved response ([Duchmann 2017](#)).

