8.2.3.10.2 Hematological Toxicity

Patients with neutropenia or thrombocytopenia as a consequence of their disease do not require treatment interruptions for myelosuppression. Dose modifications in these patients should be considered on a case-by-case basis and discussed with the Medical Monitor. The following guidelines can be used for these patients:

- Patients with a response and pre-cycle counts of neutrophils $> 1000/\mu\text{L}$ and platelets $> 50,000/\mu\text{L}$ who have sustained low counts of neutrophils $< 500/\mu\text{L}$ and/or platelets $< 20,000/\mu\text{L}$ for more than 2 consecutive weeks in the current cycle, may receive a subsequent cycle of tagraxofusp, at the Investigator's discretion.
- If there are persistent blasts in the peripheral blood or $> 5\%$ blasts in the bone marrow, continue treatment regardless of neutrophil and platelet count and give supportive care as needed.
- If no evidence of leukemia in the bone marrow, consider holding (postponing) therapy until recovery of neutrophils to $\geq 1000/\mu\text{L}$ and platelets $\geq 50,000/\mu\text{L}$, then resume tagraxofusp according to guidelines mentioned above.

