Bone Marrow CR ⁽²⁾	Bone marrow $\leq 5\%$ myeloblasts and decrease by $\geq 50\%$ over pretreatment ² Peripheral blood: If hematologic improvement responses, they will be noted in addition to marrow CR ²
Stable disease	Failure to achieve at least PR, but no evidence of progression for > 8 weeks
Failure	Death during treatment or disease progression characterized by worsening of cytopenias, increase in percentage of bone marrow blasts or progression to a more advanced MDS FAB subtype than pretreatment
Relapse after CR or PR	At least 1 of the following: Return to pretreatment bone marrow blast percentage Decrement of $\geq 50\%$ from maximum remission/response levels in granulocytes or platelets Reduction in Hemoglobin concentration by $\geq 1.5\text{ g/dL}$ or transfusion dependence
Cytogenetic response	Complete: Disappearance of the chromosomal abnormality without appearance of new ones Partial: At least 50% reduction of the chromosomal abnormality
Disease progression	For patients with: Less than 5% blasts: $\geq 50\%$ increase in blasts to $> 5\%$ blasts 5-10% blasts: $\geq 50\%$ increase to $> 10\%$ blasts 10-20% blasts: $\geq 50\%$ increase to $> 20\%$ blasts 20-30% blasts: $\geq 50\%$ increase to $> 30\%$ blasts Any of the following: At least 50% decrement from maximum remission/response in granulocytes or platelets Reduction in Hemoglobin by $\geq 2\text{ g/dL}$ Transfusion dependence
Survival	Endpoints: Overall: death from any cause Event free: failure or death from any cause PFS: disease progression or death from MDS DFS: time to relapse Cause-specific death: death related to MDS

Adapted from Cheson, et al. Blood 2006; 108(2):419-25.

Deletions to the IWG response criteria are not shown. To convert hemoglobin from g/dL to g/L, multiply g/dL by 10.

MDS: myelodysplastic syndromes. Hgb: hemoglobin. CR: complete remission. HI: Hematologic improvement. PR: partial remission. FAB: French-American-British. AML: Acute myeloid leukemia. PFS: Progression-free survival. DFS: Disease-free survival.

1 Dysplastic changes should consider the normal range of dysplastic changes (modification) (Ramos 1999)

2 Modification to IWG response criteria

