3 In some circumstances, protocol therapy may require the initiation of further treatment (e.g., consolidation, maintenance) before the 4-week period. Such patients can be included in the response category into which they fit at the time the therapy is started. Transient cytopenias during repeated chemotherapy courses should not be considered as interrupting durability of response, as long as they recover to the improved counts of the previous course.

Table 8: Stage 3A: 2015 MDS/MPN Response Criteria (Savona 2015)

Criteria for measurement of treatment response in adult MDS/MPN

CR (presence of all of the following improvements)¹

- Bone marrow:
 - $\leq 5\%$ myeloblasts (including monocytic blast equivalent in case of CMML)
 - Normal maturation of all cell lines and return to normal cellularity¹
 - Osteomyelofibrosis absent or equal to “mild reticulin fibrosis” (\leq grade 1 fibrosis)²
- Peripheral blood³
 - WBC $\leq 10 \times 10^9$ cells/L
 - Hgb ≥ 11 g/dL
 - Platelets $\geq 100 \times 10^9/L; \leq 450 \times 10^9/L$
 - Neutrophils $\geq 1.0 \times 10^9/L$
 - Blasts 0%
 - Neutrophil precursors reduced to $\leq 2\%$
 - Monocytes $\leq 1 \times 10^9/L$
- Extramedullary disease: Complete resolution of extramedullary disease present before therapy (e.g. cutaneous disease, disease-related serous effusions), including palpable hepatosplenomegaly
- Persistent low-level dysplasia is permitted given subjectivity of assignment of dysplasia¹

Note: Provisional category of CR with resolution of symptoms is removed from the original criteria.³

Complete cytogenetic remission

- Resolution of previously present chromosomal abnormality (known to be associated with myelodysplastic, syndrome myeloproliferative neoplasms, or MDS/MPN), as seen on classic karyotyping with minimal of 20 metaphases or FISH⁴

Partial remission

- Normalization of peripheral counts and hepatosplenomegaly with bone marrow blasts (and blast equivalents) reduced by 50%, but remaining $> 5\%$ of cellularity except in cases of MDS/MPN with $\leq 5\%$ bone marrow blasts at baseline

Marrow response

- Optimal marrow response: Presence of all marrow criteria necessary for CR without normalization of peripheral blood indices as presented above
- Partial marrow response: Bone marrow blasts (and blast equivalents) reduced by 50%, but remaining $> 5\%$ of cellularity, or reduction in grading of reticulin fibrosis from baseline on at least 2 bone marrow evaluations spaced at least 2 months apart

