 - Increase in cytogenetic burden of disease by ≥ 50% in partial cytogenetic remission via FISH or classic karyotyping.
- New extramedullary disease.
 - Worsening splenomegaly:

Progressive splenomegaly that is defined by IWG-MRT: the appearance of a previously absent splenomegaly that is palpable at > 5 cm below the left costal margin or a minimum 100% increase in palpable distance for baseline splenomegaly of 5-10 cm or a minimum 50% increase in palpable distance for baseline splenomegaly of > 10 cm

Extramedullary disease outside of the spleen to include new/worsening hepatomegaly, granulocytic sarcoma, skin lesions, etc.

Minor criteria

- Transfusion dependence⁴
- Significant loss of maximal response on cytopenias ≥ 50% decrement from maximum remission/response in granulocytes or platelets
- Reduction in Hgb by ≥ 1.5 g/dL from best response or from baseline as noted on complete blood count
- Increasing symptoms as noted by increase in ≥ 50% as per the MPN-SAF TSS⁵
- Evidence of clonal evolution (molecular)⁶

1 Blasts as measured from the bone marrow.

2 Patients with development of acute myeloid leukemia from MDS/MPN; 20-30% blasts may be allowed on some clinical trials for patients with MDS/MPN.

3 Increase in cytogenetic burden of disease by ≥ 50% (via FISH or classic karyotyping). Given variability of fluorescent probes used in FISH, cytogenetic normalization via FISH will depend on specific probes used.

4 Transfusion dependency is defined by a history of at least 2 units of red blood cell transfusions in the past month for a hemoglobin level < 8.5 g/dL that was not associated with clinically overt bleeding. Cytopenia resulting from therapy should not be considered in assessment of progression.

5 MPN-SAF TSS validation among patients with MDS/MPN is currently under way (R.A. Mesa, personal communication, 2014).

6 The identification of new abnormalities using single nucleotide polymorphism arrays or sequencing or a clearly significant increase in mutational burden of a previously detected abnormality. Precise criteria for defining new abnormalities and what exactly constitutes a significant increase in mutational burden are open to interpretation; we suggest that this criterion should be used conservatively based on current evidence.

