3.5. Methods of Pooling Data

Disposition, baseline, and safety summaries will be displayed by dose as well as by disease and trial stage. Tabulations presented by dose will include a summary of each dose level for MF and for CMML separately.

7 µg/kg/day	9 µg/kg/day	12 µg/kg/day	Overall
-------------	-------------	--------------	---------

Tabulations presented by disease and trial stage will include a summary of each stage for MF (Stages 1 and 2) and for CMML (Stages 1, 2, and 3A).

MF			CMML			
Stage 1 (N=xx)	Stage 2 (N=xx)	Overall (N=xx)	Stage 1 (N=xx)	Stage 2 (N=xx)	Stage 3A (N=xx)	Overall (N=xx)

For myelofibrosis patients, summaries will be displayed by Dynamic International Prognostic Scoring System (DIPSS)-Plus Risk for treatment naïve and for relapsed/refractory patients separately.

Intermediate-1	Intermediate-2	High	Overall
----------------	----------------	------	---------

For chronic myelomonocytic leukemia patients, summaries will be displayed by CMML Type for treatment naïve and for relapsed/refractory patients separately.

CMMI-1	CMMI-2	Overall
--------	--------	---------

One patient with SM was treated in Stage 2 and will be presented in data listings. No patients with PED were treated so no separate tabulations or listings will be presented.

Summaries of efficacy results will be displayed separately for MF and CMML patient groups treated at 12 µg/kg, and separately for patients treated at 7 or 9 µg/kg. Efficacy results for MF patients will be presented separately for treatment-naïve and relapsed/refractory patients. For myelofibrosis patients, summaries will be displayed by DIPSS-Plus Risk for treatment naïve and for relapsed/refractory patients separately. For chronic myelomonocytic leukemia patients, summaries will be displayed by CMML Type for treatment naïve and for relapsed/refractory patients separately.

Treatment Naïve (N=xx)	Relapsed/ Refractory (N=xx)	Overall (N=xx)
---------------------------	--------------------------------	-------------------

Efficacy summaries of investigator report response data for CMML patients will be presented separately for treatment-naïve and relapsed/refractory patients, with Stages 1 and 2 presented separately from Stage 3A patients.

Stages 1-2			Stage 3A		
Treatment	Relapsed/ Refractory	Overall	Treatment	Relapsed/ Refractory	Overall
Naïve (N=xx)	(N=xx)	(N=xx)	Naïve (N=xx)	(N=xx)	(N=xx)

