4.3.3. Progression-Free Survival

Progression-free survival is defined as the time from the date of first infusion of tagraxofusp to the date of PD or death from any cause, whichever occurred first. For patients who receive SCT, PFS will include time to PD or death post-transplant. Patients who do not progress and are still alive at the time of analysis will be censored on the date of last disease assessment recorded prior to the analysis date. If patient starts other anticancer therapies (with the exception of SCT), they will be censored at the latter of the date of last treatment with tagraxofusp or date of last disease assessment recorded that occurred prior to the start of the new therapy. The distribution for PFS will be estimated by Kaplan-Meier methodology and the 25th percentile, median, 75th percentile, number and percentage of events and censored observations, and appropriate 95% CIs will be presented.

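### Stage 2 CMML: PFS can count drug-related cytopenia alone as progression, which Stage 3A rules out, and the SAP does not keep the two PD rules apart

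*SAP*

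**What the plan says.** Protocol 11.12 assigns different response criteria by stage. Stage 2 CMML uses IWG MDS 2006 (protocol 18.1, Table 7; SAP Table 8-3). Stage 3A uses MDS/MPN 2015 (protocol 18.1, Table 8; SAP Table 8-4).

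- **Stage 2 CMML progression.** Besides the blast-count thresholds, Table 7 lists three items, any one of which is enough: "At least 50% decrement from maximum remission/response in granulocytes or platelets", a hemoglobin reduction of at least 2 g/dL, and transfusion dependence.
- **Stage 3A progression.** Table 8 needs two major criteria, one major and two minor, or three minor. Count loss, hemoglobin loss and transfusion dependence are all minor. A footnote adds: "Cytopenia resulting from therapy should not be considered in assessment of progression".
- **PFS.** SAP 4.3.3 counts time from first infusion "to the date of PD or death from any cause, whichever occurred first". It makes no exception by type of PD.
- **Display.** SAP 3.5 states: "Summaries of efficacy results will be displayed separately for MF and CMML patient groups treated at 12" µg/kg. Its general efficacy columns are treatment-naïve, relapsed/refractory and overall. It separates Stages 1-2 from Stage 3A only for investigator-reported response data in CMML.

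**The concern.** Protocol 4.4 names thrombocytopenia and anemia among the most common treatment-emergent events with tagraxofusp. In Stage 2 CMML, a toxicity the drug is known to cause can by itself satisfy the written definition of progression and end a patient's PFS. The same finding in Stage 3A would not be progression.

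Two things are at stake. Stage 2 CMML PFS could be shorter than the disease course warrants. And if PFS is tabulated for all CMML patients at 12 µg/kg, one curve would combine two definitions of the event, so a difference between stages could reflect the criteria instead of the patients.

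**Working it through.** The documents give no PFS sample size, event count or median, so there is no planned figure to reproduce. The check compares the texts.

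**1. The rules side by side.**

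| Finding | Stage 2 CMML (Table 7) | Stage 3A (Table 8) |
|---|---|---|
| Hemoglobin fall | ≥ 2 g/dL: PD alone | ≥ 1.5 g/dL: one minor criterion |
| Transfusion dependence | PD alone | one minor criterion |
| Granulocytes or platelets down ≥ 50% from best response | PD alone | one minor criterion |
| Cytopenia caused by therapy | no exclusion | not considered |

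**2. Does Table 7 remove drug effects elsewhere?** Its only cytopenia provision is footnote 3: "Transient cytopenias during repeated chemotherapy courses should not be considered as interrupting durability of response", provided the counts recover. That protects the duration of a response. It does not mention PD, sustained falls or PFS, and SAP 4.3.3 does not refer to it.

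**3. A hypothetical patient.** Hemoglobin drops from 10.0 to 8.0 g/dL, judged drug-related, with blasts, spleen, other counts and symptoms unchanged.
- Stage 2: 10.0 − 8.0 = 2.0, which meets ≥ 2 g/dL. This is PD and a PFS event.
- Stage 3A: 2.0 exceeds 1.5, giving one minor criterion where three are needed without a major one. Adding transfusion dependence makes two, still not PD. The therapy exclusion applies in any case.

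**4. When each item can act.** The hemoglobin and transfusion items can be met by any patient. The granulocyte/platelet item is measured from maximum response, so it needs an earlier response. Table 7 asks for a response of at least 4 weeks, and the first scheduled assessment is at the end of Cycle 1 (day 21). On the ordinary reading the earliest such PD is therefore about day 21 + 28 = 49.

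**5. Can the stages be combined?** SAP 3.5 neither requires nor prevents a PFS table over all CMML patients at 12 µg/kg. The stage columns are prescribed for response data, not for PFS.

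**6. Direction and size.** Recording toxicity as PD can move a patient's PFS time earlier, never later. SAP 1.1.2 gives about 30 patients per Stage 2 cohort. With no censoring, k affected patients lower the curve by k/30 at times lying between their recorded and true event dates:
- k = 0: 0
- k = 1: 1/30 = 3.3 percentage points
- k = 2: 2/30 = 6.7 points
- k = 5: 5/30 = 16.7 points

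The values of k are assumptions; the documents supply none. The median moves only if affected patients are recorded before it and would otherwise have passed it.

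**The case against.** **What stands.** PD is recorded by the investigator, and nothing in the SAP derives it from counts by algorithm. An investigator may never have called a drug-related fall progression, so the number affected may be zero. Table 7 adapts published consensus criteria, and protocol 4.1.1 reports an expert panel preferring IWG 2006 for monitoring response, so it is defensible for the main analysis. PFS is secondary and descriptive, without type I error control, and SAP section 5 says Stage 3B will not start. Both rule sets are printed in the SAP and labelled by stage. The Stage 3A exclusion sits in a footnote to the transfusion item, though its wording is general. These points limit the weight of the concern. They do not supply the missing rule, and a combined PFS table would not show which rule each event came from.

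**Stronger readings the documents do not support.**
- *That the protocol doses Stage 2 CMML patients through falls it also calls PD.* Protocol 8.2.3.10.2 says certain responders with low counts "for more than 2 consecutive weeks in the current cycle, may receive a subsequent cycle of tagraxofusp", and that with persistent blasts sites should "continue treatment regardless of neutrophil and platelet count and give supportive care as needed". But the section is introduced for disease-related neutropenia or thrombocytopenia, is discretionary for responders, suggests holding when the marrow is clear, and omits anemia. Section 8.2 also conditions dosing on absence of PD. Patients enrolled under Amendment 6 or earlier were not reconsented (protocol 5.1), and that amendment's dosing text is not available.
- *That a frequency can be borrowed from protocol 4.1.1.* Of 79 patients in a retrospective series, "6 patients who had PD per the IWG 2006 criteria at first assessment finally achieved response". The text does not say those PDs were cytopenia, and the reference list shows the series was treated with hypomethylating agents.
- *That the median loss can be computed by placing every such PD at the end of Cycle 1.* Step 4 shows this does not fit the granulocyte/platelet item.
- *That ORR has a gap for a CR or PR after such a PD.* SAP 4.3.1 reports best response on study and does not stop at PD, so no change is needed there.

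**Conclusion.** The point holds as a minor one. By the written criteria, a cytopenia caused by the drug can alone be a PFS event in Stage 2 CMML but not in Stage 3A, and the SAP neither separates PFS by stage nor tests the effect. Any bias is towards shorter Stage 2 PFS. Its size cannot be estimated from the documents and may be zero; under the assumptions in step 6 it is about 3.3 percentage points of the curve per affected patient. ORR, OS and the Stage 3A criteria are not in question. The conclusion assumes that investigators apply Table 7 as printed and that the same criteria governed Stage 2 CMML patients enrolled under earlier amendments.

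**What to change.** 1. In SAP 3.5 and 4.3.3, present CMML PFS at 12 µg/kg separately for Stages 1-2 and Stage 3A, as is already done for response data.
2. In SAP 4.3.3, add one sensitivity PFS for Stage 2 CMML. PD met only through the granulocyte/platelet, hemoglobin or transfusion items, and attributed to therapy, is not an event. Follow-up then runs to the next qualifying PD or death, under the existing censoring rules.
3. Keep the main PFS as written.

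Listing the criterion met for each PD would help readers but is only clarification.

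**Cost.** One extra column set and one extra analysis, using counts, transfusions and marrow results already collected. Attribution to therapy is a judgment made in an open-label study, so it should be settled before the PFS results are produced. Patients who stopped at such a PD and have no later event would be censored at their last disease assessment. That censoring may be informative and could make the sensitivity PFS too long, so it should be read beside the main result, not in place of it.

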4.3.4. Overall Survival

Overall survival is defined as the time from the date of first infusion of tagraxofusp to the date of death from any cause. Patients still alive or lost to follow-up at the time of the analysis will be censored on the last date known to be alive prior to the analysis date, as determined by in-person visit or telephone contact.

Duration of follow-up is defined as the time from the date of first infusion of tagraxofusp to the last date known alive. Patients who died will be censored on the date of death.

The overall distributions for OS and follow-up durations will be estimated by Kaplan-Meier methodology in a similar manner to PFS.

4.3.5. Spleen Volume

Spleen size by MRI/CT will be summarized over time for all patients with baseline splenomegaly. The number and percentage of patients with $\geq 10\%$, $\geq 25\%$, and $\geq 35\%$ reduction in spleen volume from baseline will be summarized over time.

The maximum percent reduction from baseline in spleen size across all post-baseline visits will be summarized. A waterfall plot of the maximum percent reduction in spleen volume, spleen volume at Cycle 4 Day 21 visit, and spleen volume at Cycle 7 Day 28 will be created.

4.3.6. Tumor Symptom Score

Symptom scores will be summarized over time for all patients. The number and percentage of patients with $\geq 25\%$ and $\geq 50\%$ reduction in MPN-SAF TSS from baseline will be summarized over time.

The maximum percent reduction from baseline in score across all post-baseline visits will be summarized. A waterfall plot of the maximum percent reduction in score, score at Cycle 4 Day 21 visit, and score at Cycle 7 Day 28 will be created.

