Criteria for measurement of treatment response in adult MDS/MPN

Clinical benefit

Requires 1 of the following in the absence of progression or CR/partial response and independent of marrow response (response must be verified at ≥ 8 weeks) to be considered a clinical benefit. (Note: “Cord blood response” was corrected to “response”.)

- Erythroid response
 - Hgb increase by ≥ 2.0 g/dL
 - Transfusion independence for ≥ 8 weeks for patients requiring at least 4 packed red blood cell transfusions in the previous 8 weeks
 - Only red blood cell transfusions given based on physician’s judgement for a pretreatment Hgb of ≤ 8.5 g/dL will count in the red blood cell TI response evaluation⁵
- Platelet response
 - Transfusion independence when previously requiring platelet transfusions of at least a rate of 4 platelet transfusions in the previous 8 weeks
 - Pretreatment $\leq 20 \times 10^9/L$: increase from $< 20 \times 10^9/L$ to $> 20 \times 10^9/L$ and by at least 100%
 - Pretreatment $> 20 \times 10^9/L$ but $\leq 100 \times 10^9/L$: absolute increase of $\geq 30 \times 10^9/L^5$
- Neutrophil response
 - Pretreatment $\leq 0.5 \times 10^9/L$, at least 100% increase and an absolute increase $\geq 0.5 \times 10^9/L$
 - Pretreatment, $> 0.5 \times 10^9/L$ and $\leq 1.0 \times 10^9/L$, at least 50% increase and an absolute increase $\geq 0.5 \times 10^9/L^5$
- Spleen response
 - Either a minimum 50% reduction in palpable splenomegaly of a spleen that is at least 10 cm at baseline or a spleen that is palpable at more than 5 cm at baseline becomes not palpable
- Symptom response (improvement in symptoms as noted by decrease of $\geq 50\%$ as per the MPN-SAF TSS scoring < 20 were not considered eligible for measuring clinical benefit)⁶

- 1 Presence of dysplastic changes, which may be interpreted within the scope of normal range of dysplastic changes, may still exist in the presence of CR as allowed in MDS IWG. Marrow should exhibit age-adjusted normocellularity in CR.
- 2 If there is no significant fibrosis present on the initial bone marrow biopsy, a second biopsy is not required to prove resolution of fibrosis. Grading of fibrosis in measurement of treatment response should be according to the European Consensus System (Thiele 2005).

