4.3.7. Other Assessments of Disease Response

The proportion of subjects with $\geq 35\%$ reduction in spleen size from baseline and $\geq 50\%$ reduction in score from baseline will be summarized over time. The proportion of subjects with an anemia response for MF patients and with erythroid response for CMML patients will also be summarized over time.

For patients who were transfusion-dependent at baseline, the number and percentage of patients who achieved transfusion independence following treatment start will be summarized for any 12-week period (at any time, at C4D21-12 weeks and C7D28-24 weeks). Transfusion dependency will be for pRBCs, platelets, and both, as defined in [Section 1.2.5.1](#). The rate of transfusions will also be summarized at any time post-baseline, from pre-baseline to baseline, from baseline to Week 12, and from Week 12 to Week 24.

For patients who were Red Blood Cell Transfusion Independent at Baseline, the number and percentage of patients becoming transfusion dependent following treatment start will be summarized for any 12-week period (at any time, at C4D21-12 weeks and C7D28-24 weeks). Transfusion dependency will be summarized pRBC as defined in Section 1.2.5.1.

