- 9 Symptoms are evaluated by the MPN-SAF TSS. The MPN-SAF TSS is assessed by the patients themselves and this includes fatigue, concentration, early satiety, inactivity, night sweats, itching, bone pain, abdominal discomfort, weight loss and fevers. Scoring is from 0 (absent/as good as it can be) to 10 (worst imaginable/bad as it can be) for each item. The MPN-SAF TSS is the summation of the individual scores (0-100 scale). Symptom response requires $\geq 50\%$ reduction in the MPN-SAF TSS.
- 10 Progressive disease assignment for splenomegaly requires confirmation by MRI or CT showing a $\geq 25\%$ increase in spleen volume from baseline. Baseline values for both physical examination and imaging studies refer to pretreatment baseline and not to posttreatment measurements.

Table 8-2 Grading of Myelofibrosis

MF-0	Scattered linear reticulin with no intersections (crossovers) corresponding to normal BM.
MF-1	Loose network of reticulin with many intersections, especially in perivascular areas.
MF-2	Diffuse and dense increase in reticulin with extensive intersections, occasionally with focal bundles of thick fibers mostly consistent with collagen, and/or focal osteosclerosis. ¹
MF-3	Diffuse and dense increase in reticulin with extensive intersections and coarse bundles of thick fibers consistent with collagen, usually associated with osteosclerosis. ¹

Adapted from Arber et al, Blood 2016; 127(20): 2391-2405

Semiquantitative grading of BM fibrosis (MF) with minor modifications concerning collagen and osteosclerosis. Fiber density should be assessed only in hematopoietic areas.

1. In grades MF-2 or MF-3 an additional trichrome stain is recommended.

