- Normalization of peripheral counts and hepatosplenomegaly with bone marrow blasts (and blast equivalents) reduced by 50%, but remaining > 5% of cellularity except in cases of MDS/MPN with $\leq 5\%$ bone marrow blasts at baseline

Marrow response

- Optimal marrow response: Presence of all marrow criteria necessary for CR without normalization of peripheral blood indices as presented above
- Partial marrow response: Bone marrow blasts (and blast equivalents) reduced by 50%, but remaining > 5% of cellularity, or reduction in grading of reticulin fibrosis from baseline on at least 2 bone marrow evaluations spaced at least 2 months apart

Clinical benefit

Requires 1 of the following in the absence of progression or CR/partial response and independent of marrow response (response must be verified at ≥ 8 weeks) to be considered a clinical benefit. (Note: “Cord blood response” was corrected to “response”.)

- Erythroid response
 - Hgb increase by ≥ 2.0 g/dL
 - Transfusion independence for ≥ 8 weeks for patients requiring at least 4 packed red blood cell transfusions in the previous 8 weeks
 - Only red blood cell transfusions given based on physician’s judgement for a pretreatment Hgb of ≤ 8.5 g/dL will count in the red blood cell TI response evaluation⁵
- Platelet response
 - Transfusion independence when previously requiring platelet transfusions of at least a rate of 4 platelet transfusions in the previous 8 weeks
 - Pretreatment $\leq 20 \times 10^9/L$: increase from $< 20 \times 10^9/L$ to $> 20 \times 10^9/L$ and by at least 100%
 - Pretreatment $> 20 \times 10^9/L$ but $\leq 100 \times 10^9/L$: absolute increase of $\geq 30 \times 10^9/L$ ⁵
- Neutrophil response
 - Pretreatment $\leq 0.5 \times 10^9/L$, at least 100% increase and an absolute increase $\geq 0.5 \times 10^9/L$
 - Pretreatment, $> 0.5 \times 10^9/L$ and $\leq 1.0 \times 10^9/L$, at least 50% increase and an absolute increase $\geq 0.5 \times 10^9/L$ ⁵
- Spleen response
 - Either a minimum 50% reduction in palpable splenomegaly of a spleen that is at least 10 cm at baseline or a spleen that is palpable at more than 5 cm at baseline becomes not palpable

Symptom response (improvement in symptoms as noted by decrease of $\geq 50\%$ as per the MPN-SAF TSSscoring < 20 were not considered eligible for measuring clinical benefit)⁶

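### For Stage 3A CMML, the symptom-score reduction rates and waterfall include patients with TSS below 20, whom the adopted response criteria treat as ineligible

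*SAP*

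**What the plan says.** SAP 4.3.6 sets the population: "Symptom scores will be summarized over time for all patients". The numbers and percentages with at least a 25% and at least a 50% "reduction in MPN-SAF TSS from baseline will be summarized over time". It adds a best-change summary: "The maximum percent reduction from baseline in score across all post-baseline visits will be summarized", shown also as a waterfall. No minimum baseline score is given. SAP 4.3.7, on other assessments of disease response, takes a spleen-size reduction of at least 35% together with a 50% "reduction in score from baseline will be summarized over time", again without a floor.

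The Stage 3A criteria differ. In SAP Table 8-4 (Section 8.2), symptom response needs a TSS decrease of at least 50%, and patients with scores under 20 "were not considered eligible for measuring clinical benefit". Protocol Table 8 (Section 18.1) has the same rule: "scoring < 20 were not considered eligible for measuring clinical benefit". The line is garbled and does not print the word baseline, but baseline is its natural reading. Table 8-4 also requires clinical benefit to be verified at 8 weeks or later.

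SAP 4.3.1 reports CMML symptom response separately and points to Section 8.2, where the exclusion sits.

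The MF criteria (SAP Table 8-1) ask only for a 50% TSS reduction, with no floor. The Stage 2 CMML criteria (Table 8-3) contain no symptom response.

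**The concern.** On the scale in question ("The MPN-SAF TSS is the summation of the individual scores (0-100 scale"), a fall from 4 to 2 is a 50% reduction, though it is two points out of 100. At baseline 0 a percent change is undefined, and the SAP does not say what happens to such patients.

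The SAP restricts comparable counts elsewhere to patients who have something to lose. Spleen volume is summarized in those with baseline splenomegaly (4.3.5), and marrow-blast reduction in CMML patients with baseline blasts of at least 5% (4.3.8.1). The TSS displays lack that step.

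Symptom response and symptom score are among the clinical benefits that Stage 3A sets out to evaluate (SAP 1.1.3.3). As written, the report could carry two Stage 3A rates for a 50% TSS reduction, one with the exclusion (4.3.1) and one without (4.3.6), and nothing in the SAP would warn the reader that they count different patients.

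**Working it through.** **The plan's own figure.** The documents give no figure for the TSS counts. The nearest is the Stage 3A statement in SAP 3.1.2 that 10 patients with a true response rate of 0.15 give at least one response with 80% probability: 1 − 0.85^10 = 0.803. It reproduces and does not depend on this point.

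**Inputs.** From the SAP: the 25% and 50% cuts (4.3.6), the 0-100 scale (Table 8-1, note 9) and the threshold of 20 (Table 8-4). Assumed: no true change, and change distributed N(0, SD) with SD of 3, 5, 8 or 10 points.

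**Single visit.** The chance that a patient with baseline b shows a fall of at least the fraction f is P = Φ(−f·b/SD). A 50% fall is 4 points from baseline 8 and 10 points from baseline 20. With SD 5, for example, Φ(−4/5) = 0.212 and Φ(−10/5) = 0.023.

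| Baseline | Cut | SD 3 | SD 5 | SD 8 | SD 10 |
|---|---|---|---|---|---|
| 8 | 50% | 0.091 | 0.212 | 0.309 | 0.345 |
| 20 | 50% | <0.001 | 0.023 | 0.106 | 0.159 |
| 30 | 50% | <0.001 | 0.001 | 0.030 | 0.067 |
| 8 | 25% | 0.252 | 0.345 | 0.401 | 0.421 |
| 20 | 25% | 0.048 | 0.159 | 0.266 | 0.309 |

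**Best of several visits (4.3.6 only).** A simulation used integer scores clipped to 0-100, noise in the baseline measurement as well, and SD of change 3 / 5 / 8. The chance that the best of four visits shows a 50% reduction is 0.20 / 0.48 / 0.70 for a true score of 8, and 0.00 / 0.03 / 0.21 for a true score of 20.

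**Illustration of a rate.** Assume 20 patients with no true change, 8 at baseline 8 and 12 at baseline 30. With SD 5, the expected number of 50% reductions at one visit is 8 × 0.212 + 12 × 0.00135 = 1.71, or 1.71/20 = 8.6%. With the floor it is 0.016 among 12, or 0.1%. With SD 3 the rates are 3.6% and 0.0%; with SD 8 they are 14.2% and 3.0%. At the 25% cut with SD 5, the expected counts are 3.56 of 20 (17.8%) and 0.80 of 12 (6.7%). The floor therefore removes most of the noise at the 50% cut but much less at the 25% cut. The baseline mix is invented for the illustration; the documents give none.

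**The case against.** The case on the other side is substantial, and much of it stands.

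- **4.3.6 does not call its counts responses.** Stage 3A symptom response proper is in 4.3.1, under criteria that carry the exclusion and the 8-week verification. A reader might infer that noise enters that response rate or the ORR. It does not if Section 8.2 is followed, and CR and PR in Table 8-4 contain no TSS criterion.
- **The threshold of 20 is not general.** A reader might want it applied to every TSS summary. For MF that would depart from Table 8-1 and from the Stage 2 MF endpoint of a 50% reduction at week 24 (SAP 1.1.3.2), neither of which has a floor.
- **The Stage 3A activity criterion.** A reader might infer that the 4.3.7 measure is that criterion, so that noise alone could declare activity. SAP 3.1.2 speaks of spleen-volume reduction that correlates with symptom improvement; it sets no 35% or 50% threshold and does not refer to 4.3.7. Section 4.3.7 can be read as one joint measure or as two. If joint, a TSS fluctuation cannot qualify a patient without the spleen reduction. Its results are also shown over time, so the best-of-visits inflation belongs to 4.3.6 alone.
- **The direction is not certain.** Under SAP 3.10, patients with missing results stay in the denominator, which dilutes the percentage. If baseline-0 patients are kept there too, they dilute it further.
- **The assumptions are unsupported by the documents.** The SD has no source in them, and holding it constant near the bottom of a bounded scale is a simplification.
- **The consequence is limited.** Stage 3A enrollment was not continued, Stage 3B was not started, and only descriptive analyses remain (SAP 5). Baseline TSS is summarized (4.2) and by-patient listings are planned (4.3). The table shells are in a separate document and may settle the denominators.

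What remains is that the SAP text, followed as written, gives Stage 3A percent-reduction rates in a population that its own criteria do not accept for that purpose.

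**Conclusion.** The point holds for the Stage 3A CMML descriptive summaries: the threshold rates and best-reduction waterfall in 4.3.6, and the 50% score reduction in 4.3.7. With no true change and an assumed SD of 3-10 points, a 50% fall at one visit has a chance of about 9-35% from baseline 8, against under 0.1% to 16% from baseline 20. The contrast holds across that range, but its effect on a reported rate cannot be stated without the baseline distribution, the real SD and the handling of missing scores. The conclusion also rests on reading the Table 8-4 line as referring to baseline score. It is worth correcting because it is inexpensive and removes a conflict with the symptom response in 4.3.1.

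**What to change.** For Stage 3A CMML only, present the 25% and 50% TSS rates, the TSS waterfall and the 4.3.7 score measure in patients with baseline TSS of at least 20, with that subset as the stated denominator. Give absolute change in TSS for all patients. Baseline-0 patients then drop out of the Stage 3A percent-change displays. Write the word baseline into the Table 8-4 line, and say whether 4.3.7 is one joint measure or two. Leave the MF summaries as they are.

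The restricted 4.3.6 rate can still differ from 4.3.1, because only the latter requires verification at 8 weeks; a footnote should say so.

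The cost is SAP wording, a subset flag and a smaller denominator. SAP 3.5 already separates MF from CMML efficacy, but it states the Stage 3A split explicitly only for investigator-reported response, so the TSS tables may also need a Stage 3A column.
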